2. The drug that is undergoing investigation is lawfully marketed as a prescription drug product, and the intention of the investigation is NOT to support a significant change in the advertising for the product.	
3. The investigation does NOT involve a route of administration or dosage level or use in populations or other factor that significantly increases the risks (or decreases the acceptability of the risks) associated with the use of the drug product	
2. The investigation will be conducted in compliance with the requirements for institutional (HIC) review and with the requirements for informed consent of the FDA regulations (21 CFR Part 50 and 21 CFR Part 56).	
3. The investigation will be conducted in compliance with the requirements regarding promotion and charging for investigational drugs.	

2. **Background Information:** Provide a description of previous human use, known risks, and data addressing dosage(s), interval(s), route(s) of administration, and any other factors that might influence risks. If this is the first time this drug is being administered to humans, include relevant data on animal models.

In a previous medication development project (R01-DA27132, PI: [name]), we conducted a human laboratory study to assess GUA dosing and its effects on provoked craving, anxiety stress physiology and cognitive flexibility. Men and women with Cocaine Use Disorder and co-occurring substance abuse (non opiates), were admitted on an inpatient treatment unit and treated with GUA or placebo (PBO) using a 14-day titration in a randomized double blind manner (Fox and [name], 2014). Guanfacine at 2 mgs/day versus placebo was able to lower peripheral sympathetic arousal and drug cue-induced craving but did not address stress-induced drug craving in 42 SUD men and women (25). Basal attenuation in norepinephrine ($p < .05$), heart rate ($p = .001$), and blood pressure (SBP: $p < .02$; DBP: $p = .01$) was seen in men and women given GUA, compared with the placebo group.

In preparation for the proposed study, [name] compared guanfacine (3mg/day) versus placebo in a randomized, double blind laboratory study of SUD men (N=29) and women (N=13). After the 14-day dosing titration period and at the full 3mgs/day dose, participants were exposed to 3, 10-minute personalized guided imagery procedures (i) stress, (ii) drug cue, (iii) combined stress / cue, one per day, across three consecutive days in a randomized and counterbalanced order (Fox et al., 2014); (Fox and [name], 2014). Guanfacine was found to be safe and well tolerated in both men and women. Drug Group X Sex X Time-point interactions were observed for cocaine craving, alcohol craving and anxiety indicating attenuation of Drug craving (cocaine, nicotine and alcohol) as well as anxiety was observed in guanfacine compared with the placebo group immediately following all three provocation conditions, but only in the women not the men. A Drug Group X Sex interaction for negative mood, again indicated a decrease in negative affect following all three imagery conditions and time-points in the SUD

women on GUA but not men (106). Guanfacine also attenuated basal heart rate in males and females, but to a greater extent in females and decreased stress-induced heart rate in SUD women only. In contrast, a main effect of Drug Group for nicotine craving showed that guanfacine was able to reduce craving in both men and women administered guanfacine compared with placebo. [name] also assessed the Stroop task at baseline and immediately following exposure to all three provoked imagery conditions (stress, stress/cue, cue/cue). Findings indicated that GUA (3mgs/day) improved stress and cue- provoked Stroop performance relative to placebo but only in women and not in men.

In the previous work with 3-week treatment of GUA (3mgs/day) versus placebo discussed above, [name] found it to be safe and well tolerated. In the initial study (25), the most common side effects were mild tiredness and fatigue (guanfacine 24%; placebo: 8%) and headaches (guanfacine 18%; placebo 8%). All symptoms dissipated over time without further intervention. Side effects from a dose-ranging study comparing placebo, 2 and 3 mg/day of guanfacine (26) (106) indicated mild symptoms which dissipated rapidly without intervention in 7/21 individuals in the placebo group (33.33%), 5/12 individuals in the guanfacine (2mg) group (41.7%) and 4/11 individuals in the guanfacine (3mg) group (36.4%). Furthermore, there were no significant blood pressure differences across medication and placebo groups. Also, there were no significant sex differences in reported side effects.

In preparation for this proposal, [name] conducted a randomized, double-blind, 8-week pilot study of GUA (3mgs/day) with treatment seeking CUD men and women (n=7: 5M/2F) vs placebo (n=7: 4M/3F). Using the same 16-day titration schedule used previously and proposed in the current project, GUA plasma levels were assessed as at weeks 4 and 8 in the outpatient study as well as in the inpatient study described above. GUA levels obtained in the outpatient pilot were comparable to levels to those from the inpatient study described above. These data suggest that generic GUA with bid dosing was acceptable, and patients showed high medication compliance in the outpatient setting.

Together, data indicates guanfacine 3 mg/day to be safe and tolerable with regard to assessing target engagement and validation across multiple sites in SUD women.

3. **Source:** Identify the source of the drug or biologic to be used.

GUA pills will be obtained from Watson Pharmaceuticals by the Investigational Drug Service (IDS) at Yale-New Haven Hospital (YNHH). The research pharmacist will make up identical active and placebo capsules for medication administration for both sites. Medications will be shipped to Stony Brook from Yale for randomization and dispensing at the Stony Brook site. Medication administration will occur at 8am and 8pm each day to standardize the time of administration.

a) Is the drug provided free of charge to subjects? YES NO
If yes, by whom? IDS at YNHH

1. **Storage, Preparation and Use:** Describe the method of storage, preparation, stability information, and for parenteral products, method of sterilization and method of testing sterility and pyrogenicity.
Yale research staff will pick up the prepared capsule blister packs from IDS and disperse to subjects at their outpatient appointments.

Check applicable Investigational Drug Service utilized:

YNHH IDS

CMHC Pharmacy

West Haven VA

PET Center
 Other:

None

Note: If the YNHH IDS (or comparable service at CMHC or WHVA) will not be utilized, explain in detail how the PI will oversee these aspects of drug accountability, storage, and preparation.

2. Use of Placebo: Not applicable to this research project

If use of a placebo is planned, provide a justification which addresses the following:

a) Describe the safety and efficacy of other available therapies. If there are no other available therapies, state this.
 No other available FDA medications for co-occurring SUDs in women, thus use of placebo is justified.

b) State the maximum total length of time a participant may receive placebo while on the study.
 10 weeks

c) Address the greatest potential harm that may come to a participant as a result of receiving placebo.
 No known risks

d) Describe the procedures that are in place to safeguard participants receiving placebo.
 n/a

3. Continuation of Drug Therapy After Study Closure Not applicable to this project

Are subjects provided the opportunity to continue to receive the study drug(s) after the study has ended?

Yes If yes, describe the conditions under which continued access to study drug(s) may apply as well as conditions for termination of such access. *Write here*

NO If no, explain why this is acceptable. *Write here*

B. DEVICES

N/A

SECTION III: RECRUITMENT/CONSENT AND ASSENT PROCEDURES

1. Targeted Enrollment: Give the number of subjects:

a. Targeted for enrollment at Yale for this protocol: 50
 b. If this is a multi-site study, give the total number of subjects targeted across all sites: 100

2. Indicate recruitment methods below. Attach copies of any recruitment materials that will be used.

 Flyers	 Internet/web postings	 Radio
 Posters	 Mass email solicitation	 Telephone

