positive effects in women but not in men (Fox et al., 2012; [name] et al., 2011). Preliminary data also showed that GUA 3 mg/day (bid dosing) vs. placebo led to higher cocaine-negative urines in an 8-week outpatient setting only in women and not men.

4. **Research Plan:** Summarize the study design and research procedures using non-technical language that can be readily understood by someone outside the discipline. **Be sure to distinguish between standard of care vs. research procedures when applicable, and include any flowcharts of visits specifying their individual times and lengths.** Describe the setting in which the research will take place.

The current study will test **GUA (3 mg/day) vs Placebo (PBO)** in a 10-week clinical trial across 2 sites in a total of 100 SUD women.

All participants will be titrated to steady-state medication levels over 2 weeks followed by a **7-week treatment period using a standard cognitive behavioral relapse prevention** with medication management and contingency management (CM) for treatment attendance. A 5-day taper will be implemented in week 10. All participants will also take part in **two laboratory challenge test sessions**: one at pre-treatment (pre-tx) and one during week 9 of treatment, to assess provoked drug craving and cognitive flexibility under stress, drug cue and neutral cue conditions in a randomized and counterbalanced order.

Pre-treatment Intake Procedures: Following the initial telephone screening, eligible participants will meet with the research staff to obtain written informed consent. Subjects will complete 2-3 intake appointments, and during these appointments they will be consented, screened of substance use, and provide demographic and psychiatric data. Physical examinations, blood work, a urine test, and a breathalyzer test will also be completed. All subjects will meet with the study physician, and if deemed eligible, after discussion of risk and benefits, subjects will be randomized into the study.

Randomization: Eligible subjects will then be randomized in a double blind manner to either placebo or 3 mg/day (bid dosing) of GUA balancing the patients on age, education, race, ADHD and severity of drug use.

Medication Titration Period (wk 1-3): Following a 3-day abstinence period, a 2-week titration period, previously found to be safe and with only mild adverse effects (Fox et al., 2014; Fox et al., 2012; Milivojevic et al., 2017) will be initiated (see Table 1).

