Laboratory Challenge Component: An identical laboratory challenge session will be conducted in the initial week of outpatient treatment Week 0, prior to medication, and again in Week 9. Our standard imagery script development procedures will be used to develop the stress, drug cue and neutral relaxing imagery scripts. The stress imagery script will be based on participants' description of a recent personal event experienced as "most stressful", and determined as such by rating it above 8 on a 10-point stress scale. These may include breakup with a significant other, marital conflict or job-related stress. A drug cue script will be developed based on situations involving people places and things pertaining to drug use that led to wanting drug and eventual drug use (e.g., meeting drug using friend, going by a favorite bar, etc). The neutral script will be developed from a personal non-alcohol-related relaxing situation. A 5-minute 'script' of each scenario will be written using Scene Construction Questionnaires ([name], 2009) where verbal and non-verbal responses, and physiological and bodily sensations regarding the events will be obtained. A script is then written following standard format and content procedures and scripts are then recorded onto audiotape for guided imagery in the laboratory sessions ([name], 2009). On the morning of the day prior to the initial laboratory session, participants will be brought into the testing room to receive training in relaxation and imagery procedures, as well as familiarize themselves with the subjective rating forms. The 10-min relaxation training will comprise muscle relaxation procedures in order to help subjects reach a relaxed state prior to imagery exposure during the laboratory sessions.

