Data Management: Data entry will be conducted using the Web-based REDCAP direct data entry system. Both sites are fully trained and running with REDCAP and have implemented this platform in clinical outcome studies with SUD samples. Utilizing the REDCAP system will allow data to be directly collected into the Yale managed web-based system across sites with no identifying information transmitted over the internet. Field validation (e.g. no out of range/invalid responses accepted) and form validation (e.g. logically impossible responses to different questions) are built into the REDCAP system and the study data manager will conduct weekly quality control and data management. After online reviews, the data are archived onto servers and password protected with only certain members of the team having appropriate level of data access. All quality control and management issues will be addressed immediately and also discussed in the across site weekly study meetings.

Data Analysis: Data analysis will be performed under the direction of Project PIs in consultation with [name], the Yale biostatistician. Screening for data entry errors, outlier checks and assessment of missing data and testing of normality assumptions will be conducted. Transformations will be applied as necessary. We will compare the treatment groups on demographic and clinical variables using t-tests/chi-square analyses as appropriate. If any group differences are found, the specific variable will be entered as a covariate in all specific analyses. For the primary outcome, we will use significance level of 0.05. Significance levels for secondary outcomes will be adjusted using Bonferroni correction for number of analyses performed.

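### Randomisation is placed before the 3-day abstinence period and first dose, so women who leave in between would be randomised but never treated; randomising at first dispensing is a cheap improvement

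*Combined protocol and SAP*

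**What the plan says.** Section I, item 4 (Research Plan) describes two to three intake appointments ending in a visit with the study physician, and then: "if deemed eligible, after discussion of risk and benefits, subjects will be randomized into the study". The Randomization paragraph repeats the order: "Eligible subjects will then be randomized in a double blind manner to either placebo or 3 mg/day (bid dosing) of GUA". The next paragraph, on the titration period, opens "Following a 3-day abstinence period, a 2-week titration period". Abstinence is thus described after allocation and before the first dose.

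The laboratory baseline is less definite. The Laboratory Challenge paragraph says that it is "conducted in the initial week of outpatient treatment Week 0, prior to medication", and other paragraphs call it pre-treatment. None of them places it before or after randomisation.

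The inclusion and exclusion criteria (Section I, item 8) mention neither the abstinence period nor the laboratory session. They do require a positive urine for the primary disorder during a 2-week intake period, and the primary disorder is cocaine. Section I, item 13 (Statistical Considerations) needs 40 women per group, allows 20% attrition and so plans 50 per group. It defines no analysis population.

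**The concern.** Any gap between allocation and first dose is a period in which randomised women can be lost before they receive anything. Here the gap contains a 3-day abstinence period in outpatients recently positive for cocaine, and possibly a laboratory session with its own preparation visits. Some loss is plausible.

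The plan does not say how such women would be handled. If they are kept, the estimated effect shrinks towards zero. If they are dropped, the sample shrinks and the comparison is no longer strictly as randomised. They may also use up part of the attrition allowance before treatment begins. Blinding limits bias from losses at this stage, but it does not restore power.

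**Working it through.** **Inputs from the documents (Section I, item 13).** 40 evaluable per group; 20% attrition; 50 randomised per group; alpha 0.05 for the primary outcome; power 0.80; pilot effects d=1.0 (women), 0.76 (whole group) and 0.628 (men).

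**Assumptions.** The test is two-sided, since the plan does not say. A fraction q of each arm is randomised but never dosed, and q is 5%, 10% or 15%; the documents give no figure. Never-dosed women in the guanfacine arm have placebo-like outcomes. The standard deviation is unchanged.

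**The plan's own figures.** 40/(1 − 0.20) = 50 per group, as stated. With the normal approximation, n = 2(1.960 + 0.842)²/d². At d=0.628 this is 15.70/0.394 = 39.8, or 40 per group. Of the three pilot effects, only the men's gives 40; the women's d=1.0 gives 16 and the whole-group d=0.76 gives 28.

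**Reference effect.** By the exact two-sample t-test, 40 per arm gives 80% power at d=0.634. This value is solved from the plan's n and power and is not printed in the plan. It is close to 0.628.

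**Never-dosed women kept in the analysis.** The effect becomes d(1 − q). The noncentrality is d(1 − q)√(n/2), on 2n − 2 degrees of freedom. The multiplier √(n/2) is 5 for n=50 and 4.472 for n=40.

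| q | d(1 − q) | Noncentrality, n=50 | Power, n=50 | Noncentrality, n=40 | Power, n=40 |
|---|---|---|---|---|---|
| 0 | 0.634 | 3.17 | 88% | 2.84 | 80% |
| 5% | 0.602 | 3.01 | 85% | 2.69 | 76% |
| 10% | 0.571 | 2.85 | 81% | 2.55 | 71% |
| 15% | 0.539 | 2.69 | 76% | 2.41 | 66% |

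The n=40 columns describe a particular combination: 20% of women are lost from the analysis, and a fraction q of those still analysed were never dosed.

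**Never-dosed women dropped on top of 20% attrition.** The effect stays at 0.634 and n = 40(1 − q) = 38, 36 or 34 per arm. Power is 78%, 76% or 73%.

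**Never-dosed women dropped within the 20% allowance.** n stays at 40 and power stays at 80%.

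**Other effect sizes, 40 per arm with dilution.** At d=1.0, power is 99%, 98% (97.8%) and 96% for q = 5%, 10% and 15%. At d=0.76 it is 89%, 86% and 81%.

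**The case against.** Several points on the other side are sound.

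- **Laboratory baseline.** A reader might infer that the Week 0 session follows randomisation. The text fixes it only before medication, so it may already come first. Even if it comes later, a blinded baseline taken before any drug is not biased for that reason.
- **No gate.** A reader might also infer that a woman who uses cocaine in the three days, or misses the session, is refused study drug. Neither step is an eligibility criterion, and nothing in the documents denies drug to such a woman. She may simply start titration. The never-dosed group consists of women who leave, and their number is not documented.
- **Power figures.** Taking 76%, 71% and 66% as the expected loss would overstate the case. They count 20% attrition and then dilute the remainder, at an effect chosen to give exactly 80% before any loss. With all 50 per arm analysed, power remains above 80% up to q = 10%. At the women's pilot effect the loss hardly matters, although that pilot had only 2 women on guanfacine and 3 on placebo (Section II, Background Information), so it is weak reassurance.
- **Legitimate choice.** Randomising after eligibility clearance is accepted practice, and the interval may be short.

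What survives is narrower. The written order puts allocation before abstinence and first dose, the plan does not say how early losses are handled, and a later randomisation point would remove most of the problem.

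**Conclusion.** The point holds as an improvement to the design; it is not an error in the plan. As written, at least the 3-day abstinence period separates randomisation from first dose, and the place of the laboratory baseline in that sequence is left open.

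The harm runs in one direction but its size is unknown. It depends on an assumed q, on the true effect and on an analysis set that the plan does not define. At d=0.634 and q up to 15%, the cost ranges from nothing (losses already inside the 20%) to 14 percentage points (80% to 66%). With all 50 per arm analysed it is 12 points at most (88% to 76%). At d=1.0, power is at least 96% throughout.

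**What to change.** Complete the Week 0 laboratory session and the abstinence period first, then randomise at first dispensing. State this order once in the Research Plan and align the Randomization, Titration and Laboratory Challenge paragraphs with it. No clinical rule about who may start drug needs to change. All baselines are then taken before randomisation, and nearly all randomised women are treated. The few who are still randomised and not dosed need a stated place in the primary analysis set.

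The cost is mainly logistical: coded packs must be ready at each site at first dispensing. Section II (Source) already has capsules shipped from Yale to Stony Brook, with randomisation and dispensing done there, so this should be a small step. Women who leave early would then be lost before randomisation, so somewhat more women may have to be taken through Week 0 to reach 100 randomised.
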